Primary Aim 1B: Examine e-cig appeal and abuse liability (liking, craving and sensory responses in laboratory paradigm) among 18–20-year-old current regular e-cigarette users following exposure to nicotine salt containing fruit flavored e-cigarettes, with and without menthol (e.g., Strawberry Chill & Strawberry). We will test both flavors in a single session. We hypothesize that inclusion of cooling flavors in a sweet e-cigarette will be positively associated with increases in e-cigarette liking and reinforcing efficacy as well as craving for sweet-flavored e-cigarettes and negatively associated with irritation and harshness.

Exploratory Aim: Explore if e-cigarette use (# days/past month; with/without nicotine) at a 1-month follow up is related to liking cooling flavors.

Specific Aim 2 (Study 2): Examine if flavors differentially influence reward from nicotine-containing e-cigs and e-cig use behaviors among younger and older adult combustible tobacco users. Participants will rate liking, nicotine withdrawal and stimulation using the Revised Drug Effects Questionnaire (DEQ)², flavor intensity, coolness, sweetness, and irritation (burning, stinging) experienced using the generalized Labeled Magnitude Scale (gLMS)^{31,32}, and value using the Multiple Choice Questionnaire (MCQ; e-cig value)³

Primary Aim: Examine the influence of flavors (sweet, cool, tobacco) on reward (liking/wanting) from e-cigs containing one of two nicotine concentrations (6 mg/ml, 18 mg/ml; that vary in harshness), among younger and older adult combustible tobacco users following acute tobacco abstinence. We hypothesize that younger users will like/want sweet more than menthol or tobacco flavors, while older users will like/want tobacco flavors more than cool or sweet flavors. We also hypothesize that cool flavors, but not sweet flavors, will alter liking/wanting at the 18 mg/ml nicotine concentration, but not at 6 mg/ml nicotine.

Secondary Aim: Examine the influence of flavors on nicotine’s effects on stimulation, harshness, and nicotine withdrawal and e-cig value; we expect that liking/wanting for cool flavors, but not sweet or tobacco flavors, will be positively associated with nicotine-induced stimulation and withdrawal-alleviation, but negatively associated with nicotine harshness.

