Study 2 will use established experimental methods to examine if different classes of flavors (i.e., sweet, cool, tobacco), when combined with nicotine concentrations differing in harshness (6 and 18 mg/ml) alter appeal and nicotine reward among younger and older combustible tobacco users. Importantly, this study will also explore the differential influence of sweet, cool, and tobacco flavors on switching from combustible tobacco product use to e-cigarettes, among younger and older adult combustible tobacco users. The evidence generated from this novel proposal is crucial to support regulations directed at flavors in tobacco/nicotine products like e-cigs, which will likely need to strike a balance between reducing the appeal of these products for youth and enhancing their appeal for combustible tobacco users looking to switch to use of e-cigs for harm-reduction.

4. **Research Plan:** Summarize the study design and research procedures using non-technical language that can be readily understood by someone outside the discipline. **Be sure to distinguish between standard of care vs. research procedures when applicable and include any flowcharts of visits specifying their individual times and lengths.** Describe the setting in which the research will take place.

We propose 2 double-blind, placebo-controlled studies.

Study 1B: Examine the influence of sweet and cooling flavors on the appeal and abuse potential of nicotine-containing e-cigs among susceptible young adults. Forty young adults (18-20 years of age) who have used e-cig use (used at least 10x in lifetime and at least once in the past 30-days), will participate in 1 laboratory session, and receive all the exposures in table below.

Sweet (Watermelon)		
	Non-menthol	Menthol
36 mg/ml nicotine salt	S ₁ -S ₄₀	S ₁ -S ₄₀

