During the session participants will be exposed, in random order, to sweet (watermelon e-liquid) with and without menthol, in a 36mg/ml nicotine salt, as nicotine salt is currently the most common and popular nicotine formulation among young adult e-cigarette users. Each of the two exposures will consist of a single fixed-puff bout (10 puffs; each 3-sec duration, with a 30-sec inter-puff interval). These procedures were adapted from our recent work ²⁶ where we used three puff bouts to achieve sufficient and sustained increases in nicotine levels, to conduct an adequate test of nicotine exposure on outcomes of interest. As we are not examining withdrawal and craving, a single puff bout should be sufficient to capture this. Each exposure will be separated 30 minutes to allow flavor sensation to dissipate as well as give time for nicotine effects to reduce. Prior to testing, subjects will be familiarized with the sensory and hedonic rating scales.²⁷⁻³¹ Cotinine and CO levels will be used to confirm nicotine/tobacco non-use status. After each exposure, participants will rate the flavor intensity, coolness, sweetness, and irritation (burning, stinging) experienced using the generalized Labeled Magnitude Scale (gLMS)^{31,32}, and liking/disliking of the flavor sensation using the Labeled Hedonic Scale (LHS)²⁷. These procedures are adapted from our earlier work ². Follow ups: Participants will be contacted at 1-month time-points to determine changes in use of e-cigs (with and without nicotine), any health changes, and other tobacco use (number of days used/30 days) using Timeline Follow-Back methods³³⁻³⁷. We will examine whether the sensory attributes of

different flavors observed in the experimental session predicts use of nicotine-containing e-cigs, or preference for flavors, during the follow-up periods.

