1. General Labeled Magnitude Scale (gLMS)³² (Study 1, Study 2): In Study 1 gLMS ratings will be obtained following each puff exposure and in Study 2 following each 10-puff bout. Participants will rate overall intensity, sweetness, coolness, irritation using the gLMS which is a category ratio scale with 7 semantic labels: "no sensation", "barely detectable", "weak", "moderate", "strong", "very strong", and "strongest imaginable". The labels are positioned quasi-logarithmically according to their empirically determined semantic magnitudes³⁷. The gLMS will be displayed on a monitor via a custom LabView® program, and participants will make their ratings using a mouse. Ratings are numerically transformed and then used for statistical analyses.
2. Labeled Hedonic Scale (LHS)³⁸ (Study 1, Study 2): Liking will be assessed after each flavor exposure using the LHS scale. The LHS is a bipolar scale with "neutral" in the middle and 5 symmetrical semantic labels: "like/dislike slightly", "like/dislike moderately", "like/dislike very much",

"like/dislike extremely", "most liked/disliked imaginable", positioned on the scale according to their semantic magnitude. The LHS yields ratio-level data on the magnitude of liking/disliking of sensation equivalent to that produced by magnitude estimation (ME). This scale will also be displayed on a computer screen as above and numerically transformed.

3. E-cig Effects (Adapted from Drug Effects Questionnaire (DEQ)²⁶ (Study 1, Study 2): A modified version of the Drug Effects Questionnaire^{2,39} will be used in which participants will rate acute responses to the e-cig on a 0 to 100 mm scale, from "not at all" to "extremely." Following each 10-puff bout, we will assess E-cig Liking/Wanting (average of "I feel good e-cig effects", "I want more of that e-cig I received", "I feel the e-cig strength" and "I like the e-cig effect"). At baseline and following each fixed-dose bout, we will also assess Stimulant effects (average of "I feel energized" and "I feel high"), and Nicotine Withdrawal (average of "I feel sleepy", "I feel angry", "I feel irritable", "I am having difficulty concentrating", "I feel restless" and "I feel hungry").

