- 3: Severe adverse event resulting in hospitalization or prolongation of existing hospitalization, a persistent or significant disability/incapacity, or a congenital anomaly/birth defect
- 4: Life-threatening or disabling adverse event
- 5: Fatal adverse event

d. For multi-site studies for which the Yale PI serves as the lead investigator:

- i. How will adverse events and unanticipated problems involving risks to subjects or others be reported, reviewed and managed? *Write here*
- ii. What provisions are in place for management of interim results? *Write here*
- iii. What will the multi-site process be for protocol modifications? *Write here*

13. Statistical Considerations: Describe the statistical analyses that support the study design.

Power Calculations: **Study 1:** For Aim 1, we will recruit **40 subjects**. With an anticipated dropout of 10%, 36 subjects are expected to have complete data and thus we base our power calculation on this sample size. The repeated measures design (with all factors within-subject) provides 80% power at significance level 0.05 to detect an interaction of large effect size $f=0.4$ between nicotine and menthol on e-cigarette liking/disliking for sweet flavors.

Study 2: For Aim 2, we will recruit **120 subjects**: 30 younger and 30 older subjects randomized to 6mg/ml nicotine, 30 younger and 30 older to 18mg/ml. With an anticipated dropout of 10%, we base our power calculation on 108 subjects. This sample size provides 82% power at significance level 0.05 to detect an interaction of large effect size $f=0.4$ between age and flavor on e-cig liking/wanting at 18mg/ml nicotine. Similar effect sizes were observed in our previous e-cig study examining the interaction of nicotine and menthol ²⁶.

Data Management: Outcomes will be collected using scannable forms (Teleforms) provided by the YCSTP Administrative Core. The scanned forms will be processed through the Teleforms software and exported to a database on a secure computer. Error checking and data validation will occur weekly and any problems will be queried and resolved immediately. The PI's will receive monthly data quality reports to check for completeness and accuracy of key variables, as well as rates of recruitment, retention, and follow-up.

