Statistical analyses: Preliminary analyses will provide an overview of the data (e.g., randomization success, outcome distribution, missingness patterns). Outcome analyses will be intent-to-treat and using mixed-effects models. These models allow for different numbers of observations per subject, use all available data, and can handle missing-at-random data. If model assumptions will appear to be violated, we will transform the data or fit more flexible generalized linear or nonparametric mixed models. A significance level of 0.05 will be used for primary outcomes and a Bonferroni correction will be applied for secondary outcomes.

Aim 1 (Study 1). Mixed-effects model will include menthol (yes, no), and measurement time (lab, time-within-lab). A combination of random effects and structured variance-covariance matrices will be used to account for within-subject correlations. The best-fitting structure will be selected based on Akaike information criterion (AIC). We also anticipate statistically significant main effects of menthol on liking. Similar models will be used for the secondary outcomes (flavor intensity, coolness, sweetness and harshness). Mixed models will be used to test whether menthol-related alleviation in harshness and improvement in liking (subject-specific difference between menthol and no-menthol scores) predicts percent days of nicotine-containing e-cig use at 1-month and follow up.

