e-liquid mixture in Study 2 (propylene glycol [PG], vegetable glycerin [VG] and tobacco, strawberry, and menthol will consist of a concentrated flavor liquid added to a base liquid which will consist of a commonly used ration of 50% PG and 50% VG. PG is the original base liquid and is believed to produce a throat sensation ("throat hit") which mimics the feel of smoking a cigarette. VG is included to enhance the volume of vapor production, giving a greater sensory illusion of smoking. For Study 1, we will use 36mg/ml nicotine salt and for Study 2, we will use 6mg and 18 mg nicotine. In order to ensure that we have adequate amount of e-liquid, of the same constituency, we will purchase large quantities of these solutions prior to starting these experiments which will be stored at and dispensed at John Pierce Labs. As the e-liquids used in Study 1 are not currently commercially available, an ITP will be sought and approved before study activities commence.

The Suorin iShare auto battery and Suorin iShare replacement pods will be used. This e-cigarette is similar in size and function to other commercially available more popular pod style devices. All of the e-liquids will be obtained from American eLiquid Store, which manufactures all its products in Wauwatosa, WI and reports being the first e-liquid manufacturer in the US to obtain the International Organization for Standardization (ISO) 9001:2008 and Current Good Manufacturing practices (cGMP) certification. The vanilla ice e-liquids will be purchased from Mister E-Liquid located in Grand Rapids, Michigan. A new e-cigarette device will be used for each subject, and new pods will be used for each experiment. Pods will be filled with e-liquid mixtures at John Pierce Labs.

3. **Source:** Identify the source of the drug or biologic to be used. *Write here*

a) Is the drug provided free of charge to subjects? YES NO

If yes, by whom? The investigator will be purchasing the e-liquids from the American eLiquid Store website and Mister E-Liquid website for this study. These will be stored at John Pierce Labs.

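### Study 1's 80% power is stated for a nicotine-by-menthol interaction that its single nicotine level cannot estimate; the menthol effect it does test has no stated power

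*Combined protocol and SAP*

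**What the plan says.** **Power.** Section I.13, Power Calculations, Study 1, recruits 40, allows 10% dropout and works with 36 completers. It describes a repeated-measures design with every factor within subject, and claims 80% power at the 0.05 level to "detect an interaction of large effect size $f=0.4$ between nicotine and menthol on e-cigarette liking/disliking for sweet flavors". It does not state sidedness, the within-subject correlation or the number of nicotine levels.

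**Design.** Section I.4 (Study 1B) says participants "will participate in 1 laboratory session, and receive all the exposures in table below". That table has one row, 36 mg/ml, and two columns, without and with menthol. The text below it describes "sweet (watermelon e-liquid) with and without menthol, in a 36mg/ml nicotine salt". Section II.B.2 agrees: "For Study 1, we will use 36mg/ml nicotine salt and for Study 2, we will use 6mg and 18 mg nicotine".

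**Hypothesis.** Section I.1, Primary Aim 1B: "We hypothesize that inclusion of cooling flavors in a sweet e-cigarette will be positively associated with increases in e-cigarette liking".

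**Analysis.** Section I.13, Aim 1 (Study 1): "Mixed-effects model will include menthol (yes, no), and measurement time (lab, time-within-lab"). The same paragraph expects a main effect of menthol on liking, and continues: "Similar models will be used for the secondary outcomes (flavor intensity, coolness, sweetness and harshness"). Liking is therefore primary by implication, though it is not labelled so.

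**The concern.** The aim, exposure table, product section and analysis model all describe one comparison: the same person rates the same sweet liquid with and without menthol, at one nicotine strength. Only the power sentence assumes a second nicotine level.

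That sentence is the only reason given for recruiting 40 people to Study 1. If it describes a test that will not be run, nothing in the documents says what size of menthol effect the study can detect. A null result on liking could not then be set against any planned detectable difference. A reader who takes the 80% at face value would be relying on a figure that does not belong to this design. The analysis model fits the design, so what is at stake is the support for the sample size and not the validity of the test.

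**Working it through.** **1. Can the powered effect be estimated?** Interaction degrees of freedom = (nicotine levels − 1) × (menthol levels − 1) = (1 − 1) × (2 − 1) = 0. It cannot.

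**2. Can the stated 80% be reproduced if a one-degree-of-freedom interaction is supposed?** Inputs from Section I.13: 40 × 0.9 = 36 completers (correct), alpha 0.05, f = 0.4.

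| Calculation at n = 36 | Power |
|---|---|
| Two-sided F(1,35), λ = n f² = 36 × 0.16 = 5.76 | 64.6% |
| Same, λ = (n − 1) f² = 5.60 | 63.4% |
| Two-sided normal approximation | 67.0% |
| One-sided t | 76.1% |
| One-sided normal | 77.5% |
| Numerator df 2 to 6, λ = 5.76 | 54.6% down to 37.6% |
| Repeated-measures form λ = n m f²/(1 − ρ), m = 2 or 4, ρ = 0 to 0.7 | 91.0% or more |

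None gives 80%. F(1,35) needs λ of about 8.30, and with m = 2 that implies ρ = 1 − (36 × 2 × 0.16)/8.30 ≈ −0.39. A one-sided t test with all 40 subjects gives 80.0%, but the text bases the calculation on 36. The origin of the figure cannot be determined.

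**3. Power for the effect the plan tests.** With one liking rating per exposure, the menthol contrast is a paired comparison. Let dz be the mean paired difference divided by the SD of the differences. Then λ = n dz², referred to the noncentral F(1, n − 1), two-sided 0.05.

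- 80% power at n = 36: dz = √(8.30/36) = 0.480. If all 40 complete: 0.454.
- In units of the SD within a condition, d = dz × √(2(1 − ρ)). For dz = 0.48 this is 0.68, 0.57 or 0.48 SD at ρ = 0, 0.3 or 0.5. These correlations are assumptions, since the documents give none.
- Across a range of dz at n = 36:

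| dz | 0.2 | 0.3 | 0.4 | 0.5 | 0.6 | 0.8 |
|---|---|---|---|---|---|---|
| Power | 21.5% | 41.7% | 64.6% | 83.1% | 93.8% | 99.7% |

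**4. If f = 0.4 is carried over to menthol.** This is itself an assumption, because the plan attaches f to the interaction.

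- *f read as dz = 0.4:* λ = 5.76, power 64.6% two-sided or 76.1% one-sided. For 80% two-sided, 52 completers are needed (80.8%), and 52/0.9 = 57.8, so 58 recruits.
- *f read as Cohen's f for two conditions:* d = 2 × 0.4 = 0.8 and dz = 0.8/√(2(1 − ρ)).

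| ρ (assumed) | dz | λ = 36 dz² | Power |
|---|---|---|---|
| 0 | 0.566 | 11.52 | 91.0% |
| 0.3 | 0.676 | 16.46 | 97.6% |
| 0.5 | 0.800 | 23.04 | 99.7% |

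**5. Does Study 2 settle the reading?** Its stated 82% reproduces with λ = N f² at the 108/2 = 54 subjects on 18 mg/ml: 54 × 0.16 = 8.64, F(1,52), 82.2%. But that is a comparison of two age groups, for which λ = N f² is also what Cohen's f with d = 0.8 gives. It does not show which meaning applies to a paired contrast.

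**The case against.** The strongest reply is that this is one stray sentence in a coherent plan. Aim, design and model agree, no test or error rate changes, and no shortfall is shown. The plan also calls f = 0.4 large, which fits Cohen's f, where it equals d = 0.8. On that reading 36 completers have at least 91% power for menthol at any non-negative correlation. Reading f as dz = 0.4 means a difference of only 0.57, 0.47 or 0.40 SD at ρ = 0, 0.3 or 0.5, which is hard to call large.

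Much of this stands. The word large favours the reading under which 40 is ample, and nothing here shows that 40 is too few. It does not rescue the sentence. The effect size was chosen for an interaction, and the prior study cited for similar effect sizes is also described as examining the nicotine-by-menthol interaction. The documents give no expected size for menthol alone. Nor can one assume that a main effect is easier to detect: in a fully within-subject design both would be single-degree-of-freedom paired contrasts, and their power depends on sizes and variances that are not given.

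Two associated requests are minor. The power sentence's liking/disliking wording already points to the Labeled Hedonic Scale (LHS), and a session term is constant when there is only one session.

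**Conclusion.** The concern holds. The 80% power in Section I.13 refers to an effect with zero degrees of freedom in Study 1, and the menthol contrast on liking has no stated power. The statement is wrong as written and must be corrected.

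What 36 completers provide is 80% power at dz = 0.48, assuming a two-sided 0.05 test and one liking rating per exposure. Whether that is enough depends on an expected menthol effect and a within-person correlation that the documents do not supply. Plausible readings of f = 0.4 run from 65% to 99.7% over correlations of 0 to 0.5. The zero-degrees-of-freedom result rests on none of these assumptions.

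**What to change.** 1. **Section I.13, Power Calculations, Study 1.** State the menthol effect on liking that the investigators expect, in SD units, with its basis and the assumed within-subject correlation. Replace the interaction sentence with one for the paired contrast, for example: 36 completers give 80% power (two-sided 0.05) to detect a within-subject difference in liking with versus without menthol of dz = 0.48. Compare the expected effect with 0.48 and then confirm the sample size. The expected effect has to come first, because 0.48 alone is only solved back from 36.
2. **Section I.13, Aim 1 (Study 1).** Label the menthol main effect on liking as the primary Study 1 test.
3. **Tidying, same paragraph.** Name the liking measure. The LHS appears intended, but Section I.4, Assessments, also gives Study 1 the Drug Effects Questionnaire score: "Following each 10-puff bout, we will assess E-cig Liking/Wanting". Drop the lab term from the Study 1 model, since there is one session.

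If a second nicotine level was in fact intended, the design, product and model sections must be reconciled with the power section instead.

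The cost is one replaced sentence, one added sentence, one label and the small edits in item 3. Recruitment changes only if the expected effect is below about dz = 0.48. At dz = 0.4, for instance, 52 completers (58 recruits) would be needed.

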1. If an **exemption from IND filing requirements** is sought for a clinical investigation of a drug product that is lawfully marketed in the United States, review the following categories and complete the category that applies (*and delete the inapplicable categories*):

Exempt Category 1: The clinical investigation of a drug product that is lawfully marketed in the United States can be exempt from IND regulations if all of the following are yes:	
1. The intention of the investigation is NOT to report to the FDA as a well-controlled study in support of a new indication for use or to be used to support any other significant change in the labeling for the drug.	
2. The drug that is undergoing investigation is lawfully marketed as a prescription drug product, and the intention of the investigation is NOT to support a significant change in the advertising for the product.	
3. The investigation does NOT involve a route of administration or dosage level or use in populations or other factor that significantly increases the risks (or decreases the acceptability of the risks) associated with the use of the drug product	
4. The investigation will be conducted in compliance with the requirements for institutional (HIC) review and with the requirements for informed consent of the FDA regulations (21 CFR Part 50 and 21 CFR Part 56).	
5. The investigation will be conducted in compliance with the requirements regarding promotion and charging for investigational drugs.	

2. **Background Information:** Provide a description of previous human use, known risks, and data addressing dosage(s), interval(s), route(s) of administration, and any other factors that might influence risks. If this is the first time this drug is being administered to humans, include relevant data on animal models.

These devices are commercially available and therefore, we do not need an IND. We obtain all of our e-liquid from American eLiquid Store. The e-liquid mixture in Study 1 (propylene glycol [PG], vegetable glycerin [VG] and watermelon and watermelon-menthol flavorings will consist of a concentrated flavor liquid added to a base liquid which will consist of a commonly used ration of 50% PG and 50% VG. The

e-liquid mixture in Study 2 (propylene glycol [PG], vegetable glycerin [VG] and tobacco, strawberry, and menthol will consist of a concentrated flavor liquid added to a base liquid which will consist of a commonly used ration of 50% PG and 50% VG. PG is the original base liquid and is believed to produce a throat sensation ("throat hit") which mimics the feel of smoking a cigarette. VG is included to enhance the volume of vapor production, giving a greater sensory illusion of smoking. For Study 1, we will use 36mg/ml nicotine salt and for Study 2, we will use 6mg and 18 mg nicotine. In order to ensure that we have adequate amount of e-liquid, of the same constituency, we will purchase large quantities of these solutions prior to starting these experiments which will be stored at and dispensed at John Pierce Labs. As the e-liquids used in Study 1 are not currently commercially available, an ITP will be sought and approved before study activities commence.

The Suorin iShare auto battery and Suorin iShare replacement pods will be used. This e-cigarette is similar in size and function to other commercially available more popular pod style devices. All of the e-liquids will be obtained from American eLiquid Store, which manufactures all its products in Wauwatosa, WI and reports being the first e-liquid manufacturer in the US to obtain the International Organization for Standardization (ISO) 9001:2008 and Current Good Manufacturing practices (cGMP) certification. The vanilla ice e-liquids will be purchased from Mister E-Liquid located in Grand Rapids, Michigan. A new e-cigarette device will be used for each subject, and new pods will be used for each experiment. Pods will be filled with e-liquid mixtures at John Pierce Labs.

3. **Source:** Identify the source of the drug or biologic to be used. *Write here*

a) Is the drug provided free of charge to subjects? YES NO

If yes, by whom? The investigator will be purchasing the e-liquids from the American eLiquid Store website and Mister E-Liquid website for this study. These will be stored at John Pierce Labs.

4. **Storage, Preparation and Use:** Describe the method of storage, preparation, stability information, and for parenteral products, method of sterilization and method of testing sterility and pyrogenicity. After the e-liquids are received, they will be delivered and stored in appropriate light/temperature conditions at John Pierce Labs, which is a secured building. The liquids will be kept in a locked storage container in a drawer within the lab room. On the day prior to the lab sessions, a research assistant/associate/fellow who is not involved in the actual conduct of the lab sessions will fill the e-cigs. The information on randomizations to nicotine condition and flavors for each lab session has been generated by study biostatisticians. This information is stored for each participant in an individual envelope and a printed study ID on the cover. These envelopes are stored at Pierce lab along with the purchased e-liquids. The individual filling the pods will be notified of which subject ID number needs to be filled and they will then go to Pierce labs and open the envelope and fill the three pods with the appropriate e-liquids. First, they will label each pod with the study ID number and lab 1, 2 and 3 respectively. Each bottle of e-juice will be shaken vigorously prior to filling the pods. Next, they will open the top of the pod and using a mechanical pipette will load .9ml into the pipette from the e-juice bottle and carefully transfer it into the pod. This will be completed for all lab sessions in both studies. Each pod is then stored in a separate airtight bag to avoid cross contamination of flavors. The individual bags are then stored together in a larger bag labeled with the study ID number and stored back in the locked container until the lab is set to begin. Once the research assistant is ready to begin each lab, they will open the locked container, take the appropriate pod and leave the others. At the end of the lab, they will return the pod used that day to its proper bag and again return it to the lock box. The research staff will have the group randomization list and will dispense the appropriate e-liquid (nicotine level, flavor) needed for each subject.

Check applicable Investigational Drug Service utilized:

YNHH IDS

CMHC

Pharmacy

West Haven VA

PET Center None
 Other: John Pierce Lab, WCRU (West Campus Research Unit)

Note: If the YNHH IDS (or comparable service at CMHC or WHVA) will not be utilized, explain in detail how the PI will oversee these aspects of drug accountability, storage, and preparation.

5. Use of Placebo: Not applicable to this research project

If use of a placebo is planned, provide a justification which addresses the following:

- Describe the safety and efficacy of other available therapies. If there are no other available therapies, state this. *Write here*
- State the maximum total length of time a participant may receive placebo while on the study. *Write here*
- Address the greatest potential harm that may come to a participant as a result of receiving placebo. *Write here*
- Describe the procedures that are in place to safeguard participants receiving placebo. *Write here*

6. Continuation of Drug Therapy After Study Closure Not applicable to this project

Are subjects provided the opportunity to continue to receive the study drug(s) after the study has ended?

Yes If yes, describe the conditions under which continued access to study drug(s) may apply as well as conditions for termination of such access. *Write here*

NO If no, explain why this is acceptable. *Write here*

B. DEVICES N/A

- Are there any investigational devices used or investigational procedures performed at Yale-New Haven Hospital (YNHH) (e.g., in the YNHH Operating Room or YNHH Heart and Vascular Center)? Yes No

If Yes, please be aware of the following requirements:

A YNHH New Product/Trial Request Form must be completed via EPIC: Pull down the Tools tab in the EPIC Banner, Click on Lawson, Click on “Add new” under the New Technology Request Summary and fill out the forms requested including the “Initial Request Form,” “Clinical Evidence Summary”, and attach any other pertinent documents. Then select “save and submit” to submit your request; AND

Your request must be reviewed and approved in writing by the appropriate YNHH committee before patients/subjects may be scheduled to receive the investigational device or investigational procedure.

- Background Information:** Provide a description of previous human use, known risks, and any other factors that might influence risks. If this is the first time this device is being used in humans, include relevant data on animal models.

Write here

- Source:**

- Identify the source of the device to be used. *Write here*
- Is the device provided free of charge to subjects? Yes No

4. **Investigational device accountability:** State how the PI, or named designee, ensures that an investigational device is used only in accordance with the research protocol approved by the HIC, and maintains control of the investigational device as follows:

- Maintains appropriate records, including receipt of shipment, inventory at the site, dispensation or use by each participant, and final disposition and/or the return of the investigational device (or other disposal if applicable): *Write here*
- Documents pertinent information assigned to the investigational device (e.g., date, quantity, batch or serial number, expiration date if applicable, and unique code number): *Write here*
- Stores the investigational device according to the manufacturer's recommendations with respect to temperature, humidity, lighting, and other environmental considerations: *Write here*
- Ensures that the device is stored in a secure area with limited access in accordance with applicable regulatory requirements: *Write here*
- Distributes the investigational device to subjects enrolled in the IRB-approved protocol: *Write here*

SECTION III: RECRUITMENT/CONSENT AND ASSENT PROCEDURES

1. Targeted Enrollment: Give the number of subjects:

- Targeted for enrollment at Yale for this protocol: Study 1: 40 subjects; Study 2: 120 subjects
- If this is a multi-site study, give the total number of subjects targeted across all sites: *Write here*

2. Indicate recruitment methods below. Attach copies of any recruitment materials that will be used.

 Flyers	 Internet/web postings	 Radio
 Posters	 Mass email solicitation	 Telephone
 Letter	 Departmental/Center website	 Television
 Medical record review*	 Departmental/Center research boards	 Newspaper
 Departmental/Center newsletters	 Web-based clinical trial registries	 Clinicaltrials.gov
 YCCI Recruitment database	 Social Media (Twitter/Facebook):	
 XOther: TrialFacts Recruitment Services; Qualtrics Online Sample		

* Requests for medical records should be made through JDAT as described at <http://medicine.yale.edu/ycci/oncore/availableservices/datarequests/datarequests.aspx>

3. Recruitment Procedures:

Describe how potential subjects will be identified. Potential subjects will be recruited through methods previously used by our team and found to be effective. Recruitment will occur via advertising at local colleges and through Craigslist, Facebook and flyers in the community. Potential subjects will also be recruited through Trialfacts. Trialfacts is a recruitment company that specializes in research recruitment services and has been utilized in the past by Yale investigators. Services include comprehensive pre-screening, advertising. Trialfacts creates recruitment materials, landing pages, digital marketing campaigns, online advertisements. Trialfacts adheres to GCP and IRB requirements.

We additionally plan to use Qualtrics Online Sample, as a potential recruiting source used successfully in prior studies by our group. Participants will be recruited directly through Qualtrics Online Sample, a secure, market research service operated by Qualtrics, Inc. In line with procedures we have used in prior studies, Qualtrics will email invitations to panelists who they deem likely to be eligible for the study based on prior responses to a demographics survey(s) administered by Qualtrics (or its affiliate panels)

at the time participants became panelists (e.g., lifetime smoking status). Interested individuals will click on an embedded link, which will direct them to the study eligibility questions. Eligible and interested individuals will be contacted to schedule an intake appointment.

- a. We also will include flyers that advertise that persons who complete the screener form (either through the Yale Qualtrics link or via phone) will be entered into a monthly raffle for a \$50 Amazon e-gift card regardless of their eligibility status. This is to minimize the amount of blank/half-completed screeners we receive and to provide a benefit to participants who may find the screener a time burden. Monthly, all contact information will be separated from screener information into a list. Any duplicate information will be removed, and a random number generator will be used to determine the winner of the raffle. Winners will be contacted up to 3 times to inform them of their gift card winnings. If winners are not reached, then the process will be repeated to select a new winner. Non-winners will stay on the list and be eligible to win the raffle in the future. This recruitment process will be closely monitored and if not successful at producing increases in participation in the screener and eligible subjects, will be removed.
- b. Describe how potential subjects are contacted. Potential participants can contact the study to determine eligibility through phone call, text message through Text Now, or a website that will direct them to a Yale Qualtrics website where interested participants can complete a brief screening questionnaire. In addition to general screening questions, they will be asked questions regarding where they see e-cigarette ads on social media to assist with future recruitment as well as provide necessary data showing how companies are using social media to advertise. 'Microsoft Teams' will be used to maintain these screening records. If recruited via TrialFacts, participants will be scheduled via Trialfacts to receive a phone call via our Team.
- c. Who is recruiting potential subjects? The PI and research staff will recruit potential subjects.

4. Assessment of Current Health Provider Relationship for HIPAA Consideration:

Does the Investigator or any member of the research team have a direct existing clinical relationship with any potential subject?

- Yes, all subjects
- Yes, some of the subjects
- No

If yes, describe the nature of this relationship. *Write here*

